Milestone 1: NF loci (dACC or amygdala) must show higher activity during ESF-NF and higher FC with mPFC after NF training during the ESOM or ER tasks with effect sizes of $d \geq 0.4$.

Milestone 2: 20% of variance in psychological target's change (ETB, IAT) must be associated with amygdala or dACC to mPFC FC changes during the ESOM or ER tasks after NF.

If those milestones are met, during **the R33 phase**, 70 suicide attempting participants with pre-NF assessments will be randomized 1:1 to: NF or NF from a region that is not related to memory recall, labeled as "Unrelated-NF". Participants will be matched in sex, age, IQ, illness severity, suicide ideation, and abuse history if possible. Leveraging Bayesian methods to increase power, our aims and hypothesis (**H**) for the R33 phase are:

R33 Aim 1. Confirm target engagement in the NF versus the Unrelated-NF group.

H1.1: Right amygdala or dACC activity will be higher for active versus Unrelated-NF.

H1.2: Right amygdala or dACC – mPFC FC will be higher during self-processing and affect regulation tasks following active NF compared to Unrelated-NF training sessions.

R33 Aim 2. Test the relationship between neural and psychological targets' engagement and suicide ideation. H2.1: Lower affect dysregulation and abnormal self-processing behavior will follow active NF as compared to Unrelated-NF, mediated by amygdala or dACC to mPFC FC changes in self-processing and affect regulation tasks. H2.2: Higher amygdala or dACC to mPFC FC after NF will be associated with lower suicide ideation. H2.3: Affect dysregulation or abnormal self-processing behavioral changes will mediate the association between changes in FC and suicide ideation before versus after NF.

2. Background

Suicide is the 2nd leading cause of adolescent death in the U.S ²¹. Yet it is increasingly acknowledged that current evidence-based interventions for illnesses linked to suicide ideation and attempts underperform across the lifespan ^{1-7,22}.

3. Study Endpoints/Events/Outcomes

3.1 Primary Endpoint/Event/Outcome:

The primary outcome of the R61 stage will be the fMRI imaging results, behavioral tasks (IAT and EBT) and self-reported suicide ideation data. The DERS²³, RD¹²⁰ and the SPPA^{24,25} will provide self-report measures of affect dysregulation and abnormal self-processing. **The primary outcomes of the R33 stage** are similar as above but now include the C-SSRS⁹⁸ and SIQ²⁹ to test changes in suicide ideation and attempts

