14.1 Withdrawal Circumstances:

1st High risks of imminent suicide attempts, with intent, a plan and/or other conditions for study enrollment are not met. Participants can re-enroll in the study after hospitalization and/or increased levels of care in outpatient treatment and/or environmental changes (e.g., changes in school or place of residence) that leads to demonstrable stabilization and/or decrease high acute/chronic suicide risks. To re-enroll the **PI and the IMM (with possible third opinion of Pediatric Psychiatrist if needed)** must agree on the results of the study enrollment/re-enrollment conditions.

2nd Onset of significant psychotic symptoms that clearly impair judgment and ability to assent (e.g., presence of pervasive psychotic mood, visual or auditory hallucinations or other manifestations of disorganized thoughts and judgement). Note: mild, transient psychotic symptoms are allowed within the context of a depressive episode or other diagnostic category, if they do not impair the participant's ability to assent or meet criteria for a full psychotic episode as defined by the K-SADS.

3rd Onset of neurological or metabolic illness known to significantly affect brain function and structure.

4th Onset of substance dependency disorder or new evidence that symptoms are linked to substance use.

5th Onset of claustrophobia resulting in intense discomfort in the scanner that cannot be assuaged with brief anxiety decreasing interventions (e.g., talking to the experimenter/breathing and increasing verbal contact with experimenters between pulses of the scanner).

6th Known or strongly suspected SARS-COVID-2 diagnosis in the family or household or recent (1-3 days) onset of symptoms linked to a contagious illness.

7th Medication related toxicity will result in temporary withdrawal until stabilization of symptoms is ascertained via K-SADS guided assessments and/or improvement is ascertained by their attending physician.

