Patients who are hospitalized due to suicide attempt or physical illness will be temporarily discontinued/withdrawn from study participation. Patients can re-enroll and resume study activities after discharge from hospitalization, and/or if they start outpatient mental health services (e.g., medication, higher level of frequency of psychotherapy) that demonstrably lowers acute/chronic levels of high risks of imminent suicide attempt. Alternative conditions to be met for re-enrollment may be other environmental change in the home and/or school environment (e.g., changing schools or place of residence and changing caregivers) that also demonstrably lowers acute/chronic, high risks of imminent suicide attempts (see **Inclusion section**). Patients who are hospitalized at another hospital and whose medication is changed will be offered open continued neurofeedback training (after being discharged from the other hospital or/and involvement in outpatient services that decrease high imminent suicide attempt risks) until they complete the study period. Withdrawal and exclusion circumstances will be stated in consent forms.

15. Withdrawal Procedures.

15.1 Withdrawal Procedures:

Participants will be allowed to withdraw at any point during the study; all that will be required will be an email or a verbal communication via text or phone call or direct communication with any of the experimenters. Already enrolled participants' data will be part of future research and the study may continue having access and use the participant's medical records unless the

participant and/or their parents explicitly revoke our access via written communication (email or letter) or in a phone call or in person conversation. We will ask all participants whether they wish to continue giving the study access to their psychiatric records or not after withdrawal from the study (**HIPAA**).

15.2 Termination Procedures:

Participants and their parents will be called and informed verbally about the causes for termination. Alternatively, a message containing minimal information will be left in their voicemail. A brief, simple email can announce the termination without any details and with instructions to call the research staff for more specific information. Data collected till that point will still be included in research after termination.

16. Risks to Participants

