16.1 Foreseeable Risks

1. **Suicide attempt or completion risk.** Because the focus of this study is an intervention for **participants with recent suicide attempts and current suicide ideation**, the participants are at increased risk for suicide attempts, increased suicide thoughts and hospitalizations. **Participants who have attempted suicide are more likely to repeat attempts, to be hospitalized or to complete suicide compared to the general population of psychiatric patients. It is highly likely that the present study will entail reporting suicide attempts, suicide completions and hospitalizations given the population we are studying. Suicide attempts, completions or hospitalizations are thus a characteristic of the population and not a likely consequence of the proposed intervention which is of minimal risk and intrusiveness.**

2. In person suicide risk will be assessed at baseline and at the post-intervention assessment and additional precautions will be taken to help ensure participant safety. The PI ([name], PhD, L.P.) will work in conjunction with a designated pediatric psychiatrist at the Department of Psychiatry Child and Adolescent Clinic. [name] or the designated pediatric psychiatrist (if the PI is on vacation or in a conference) will be available to the PI and study staff during each of the clinical assessments, to consult with the study staff regarding the suicide risk, triage, and intervention planning. In addition to these resources, the UMN outpatient clinic has a list of 6 qualified providers that experimenters can call in case of emergency. During in-person assessments, if a 72-hour hold is warranted to ensure participants safety, security personnel are readily available in case experimenters determine that there is urgent need for escorting participants and families to the emergency department (ED) for possible hospitalization and/or further evaluation.

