Risk related to the COVID-19 virus epidemic: Face to face contact carries the risk of virus contagion. To protect all those involved, we will make sure that all our staff wash their hands thoroughly before undertaking any procedures that involves touching the participants (such as accommodating the adolescent in the scanner). We will wipe all instruments, scanners, and surfaces that the adolescent, their parents, and staff may encounter with disinfectant wipes provided by the CMRR or purchased by our study. **Meeting in person is necessary for the 2 neurofeedback training days.** Additionally, we will make every possible effort to call the participants at least 24 hours in advance so that we can screen them and their caregivers before any in-person appointment. Similarly, if any of the staff is known to be sick or potentially showing signs of illness, we will relieve that staff from face to face contact and take protective measures for the remaining personnel outlined by University of Minnesota's Office of the Vice President of Research's 'Covid-19 Guidance for the Research Community' (<https://research.umn.edu/covid-19-guidance-research/overview>). All staff that will be engaging in face-to-face contact with participants will be encouraged to vaccinate when vaccines are available.

Risks related to MRI

- a. *Claustrophobia.* If participants become uncomfortable, they will be given the option of discontinuing the study. No medications (e.g., benzodiazepines or tranquilizers) will be offered to them. The PI and/or MRI trained research staff will be present throughout the experiment and will be on hand to talk to the participants and ensure their comfort.
- b. *Magnetic pull-on metal objects.* Individuals with implanted metallic foreign bodies will be excluded.
- c. *Scanner noise.* Participants will be given sound-reducing insert plugs to wear during the scan to diminish any discomfort due to noise and to protect their hearing. A microphone and emergency signal will be provided so that they may stop the testing if they become uncomfortable or anxious at any time.
- d. *Mild symptoms.* If the participant notifies the researcher of pain or discomfort, they will be removed from the scanner.
- e. *Boredom.* Participants will view scenes from a nature movie while structural images are collected to help ease boredom during the scan.

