suicide ideation on psychometrically valid instruments (SIQ, C-SSRS); (b) random assignment, in the R33 phase, to active NF or to a Unrelated area NF condition; (c) use of HCP Lifespan imaging parameters on a Siemens 3.0 Tesla Prisma scanner, currently the best platform for high-resolution brain imaging; and (d) making all data and analytic algorithms available on a yearly basis for ready access by the wider scientific community using the GitHub platform. Full access to all data is the best means of assuring rigor and reproducibility; (e) although MDD and PTSD disorders afflict females more frequently than males, we intend to enroll both genders to explore the effect of biological variables on responses to NF training.

19. Health Information and Privacy Compliance

19.1 Select which of the following is applicable to your research:

My research does not require access to individual health information and therefore assert HIPAA does not apply.
 I am requesting that all research participants sign an approved HIPAA Disclosure Authorization to participate in the research (either the standalone form or the combined consent and HIPAA Authorization).

This will include HIV/AIDS, genetic testing, mental health diagnosis/treatment records, drug & alcohol abuse or sickle cell anemia status of the offspring/participants participating in research because these conditions/statuses can affect brain function and intellectual achievement in IQ tests, and we need to control for them.

I am requesting the IRB to approve a Waiver or an alteration of research participant authorization to participate in the research.

Appropriate Use for Research:

An external IRB (e.g., Advarra) is reviewing and we are requesting use of the authorization language embedded in the template consent form in lieu of the U of M stand-alone HIPAA Authorization. Note: External IRB must be serving as the privacy board for this option.

19.2 **Identify the source of Private Health Information you will be using for your research (Check all that apply)**

I will use the Informatics Consulting Services (ICS) available through CTSI (also referred to as the University's Information Exchange (IE) or data shelter) to pull records for me

I will collect information directly from research participants.

I will use University services to access and retrieve records from the Bone Marrow Transplant (BMPT) database, also known as the HSCT (Hematopoietic Stem Cell Transplant) database.

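### Section 14.1 offers some hospitalised participants open continued neurofeedback without holding R33 participants to their randomised condition, the two planned sessions, or a point after the Visit 4 and 5 outcomes

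*Combined protocol and SAP*

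**What the plan says.** Section 14.1 (Withdrawal Circumstances) contains two return rules. The general rule, for participants hospitalised after a suicide attempt or for physical illness, is: "Patients can re-enroll and resume study activities after discharge from hospitalization". The second covers a subset: "Patients who are hospitalized at another hospital and whose medication is changed will be offered open continued neurofeedback training". The second offer follows discharge or outpatient care that lowers the imminent risk, and lasts until the participant's study period ends. It does not mention the R61 or R33 phase, the neurofeedback locus, a number of sessions, or timing relative to any outcome visit.

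The rest of the plan describes a fixed dose. Section 1 and Table 1 set out two neurofeedback sessions, at Visits 2 and 3, and section 16 says: "Meeting in person is necessary for the 2 neurofeedback training days". For R33, section 1 says that "70 suicide attempting participants with pre-NF assessments will be randomized 1:1 to" active NF or NF from an unrelated region. Under Data Integrity, section 18 lists as an element of rigour "random assignment, in the R33 phase, to active NF or to a Unrelated area NF condition".

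On the likelihood of admissions, section 16.1 says: "It is highly likely that the present study will entail reporting suicide attempts, suicide completions and hospitalizations".

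**The concern.** The trigger for the offer occurs after randomisation and can be related to suicidality, which is what the R33 ideation outcomes measure. If a participant randomised to Unrelated-NF were given active training before Visit 4, the NF versus Unrelated-NF contrast would be diluted. If a participant in the active arm were given further active sessions, that arm would receive more than the design describes. Either would be set off by a clinical event that the intervention might itself influence.

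The hypotheses in section 18 most exposed are H2.1 (effect of NF on IAT and ETB change) and H2.3 (effect of NF on change in suicide ideation). H2.2 has no arm term but uses the same C-SSRS and SIQ scores. If such training came before Visit 3 was finished, scan day 2 activity and the post-NF connectivity measures (H1.1, H1.2) would be affected too.

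**Working it through.** The plan gives no figure for this point, so there is none to reproduce. The check has three parts.

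**1. Does any other text close the gap?**

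- Section 14.1, re-enrolment after withdrawal for suicide risk: the PI and the independent medical monitor "must agree on the results of the study enrollment/re-enrollment conditions". This governs whether a participant returns, not the locus or the dose.
- Heading of Table 1, and section 29.1: extra visits are for unfinished procedures, and repeat scans are for recovering lost data. Neither text limits the offer in 14.1.
- Section 5.1, Missing Data: imputation, mean values or elimination. Outcomes collected after open training would be observed, so this does not apply.
- Section 15.2: "Data collected till that point will still be included in research after termination". This covers data up to termination and says nothing about data after re-enrolment.
- Section 18, covariates: treatment indexes, and variables that differ between groups. Neurofeedback exposure is not named, and adjusting for a variable that arises after randomisation would not restore the randomised contrast.
- Section 18, R33 models: an indicator for the NF group is the main predictor. There is no analysis-set definition, and no rule for extra or crossed-over training.

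Nothing found ties the offer to the randomised condition, to two sessions, or to a time after Visits 4 and 5.

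**2. Which outcomes would be exposed?** This count holds only if the offer means extra or off-assignment training, given between Visits 3 and 4. The inputs are the assessments in Table 1; items 3 and 8 of the study-item table in section 5.1 agree on the numbered visits.

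| Outcome | Scheduled assessments counted | After training given between Visits 3 and 4 |
|---|---|---|
| C-SSRS, post-baseline | Visit 4, Visit 5 = 2 | 2 of 2 |
| IAT and ETB, post-NF | Visit 4, Visit 5 = 2 | 2 of 2, unless given on scan day 2, which Table 1 allows |
| SIQ, after both planned sessions | end of Visit 3, Visit 4, Visit 5 = 3 | 2 of 3 |

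SIQ appears six times after baseline: Visit 2 twice, Visit 3 twice, Visit 4 once and Visit 5 once. The first Visit 2 entry appears to precede any neurofeedback, so counting over all six would mix in a pre-training value. The row above uses only assessments after both sessions.

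Two pre-exposure measurements remain. One is the Visit 3 SIQ. The other is the C-SSRS on which section 16.4 bases re-enrolment after hospitalisation or temporary withdrawal. The latter is not in the Table 1 schedule, but it would fall after baseline and before the open training. C-SSRS is also allowed at optional contacts.

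**3. How sensitive is a trial of this size?** This is an illustration on assumptions, not an estimate. 70 randomised 1:1 gives 70 / 2 = 35 per arm. Assume a two-sample t-test at two-sided 0.05. The standardised difference detectable with 80% power is then d = 0.68. Suppose that *k* of the 35 control participants receive the full active effect. The contrast becomes d × (1 − k/35).

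| k | d × (1 − k/35) | Power |
|---|---|---|
| 0 | 0.68 | 80% |
| 1 | 0.66 | 78% |
| 2 | 0.64 | 75% |

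The documents give no value for *k*, no R33 power target, and no evidence that any crossover would be complete.

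**The case against.** The strongest reply is that the sentence only describes resuming an interrupted schedule. It follows directly on a passage about temporary withdrawal and return. *Continued*, and an end point at completion of the study period, both fit finishing what was started. Payments cover Visits 1 to 5 only, and no section describes a third session, a change of locus or open-label active training. On that reading the interval affected is Visit 2 to Visit 3, the training is the assigned Visit 3 session, and nothing is contaminated. The count for Visits 3 to 4 would then not apply. This reading is plausible and has not been ruled out. It does not settle the matter, however. The general rule on resuming study activities already covers that case, the separate offer adds the undefined word *open*, and its limit is a period rather than a number of sessions.

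It can also be said that analysis by randomised arm is the ordinary reading of a design that compares two randomised groups, and nothing suggests reclassification by training received. That stands, so the analysis half of this point is mostly a matter of writing the rule down. An analysis rule would not, however, prevent the exposure.

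Finally, few participants are likely to qualify. Section 16.1 expects hospitalisations, but not specifically outside admissions with a medication change. That stands too.

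A reader might infer that the plan moves control participants to active neurofeedback after a suicidal crisis, or that the R33 comparison is already biased. The documents support neither. They leave such a departure possible and do not describe one.

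**Conclusion.** The point holds as a minor one. Section 14.1 makes a positive offer that, on its open-label or extra-training reading, lets an event after randomisation put off-assignment or additional neurofeedback ahead of the Visit 4 and 5 outcomes in R33. Nothing elsewhere in the plan prevents this or says how to analyse it.

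Neither the size nor the direction of any bias can be computed, because the frequency, locus and number of sessions are not stated. A reader might take the counts to mean that an exposed participant has no usable post-baseline suicidality data. That goes too far, given the Visit 3 SIQ and the re-enrolment C-SSRS. The latter is taken around a clinical crisis, though, and does not replace the Visit 4 assessment.

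The conclusion rests on the text available. The consent forms are not among the documents, and a definition of *open* there cannot be excluded.

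**What to change.** Amend section 14.1 so that, in R33, a returning participant resumes only the randomised condition, within the two planned sessions. Any open or additional training is offered only after the Visit 5 outcomes have been collected.

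Add to section 18 that these participants are analysed in their randomised arm with all outcomes. Any earlier off-assignment or extra training is recorded with its date and locus. One sensitivity analysis excludes post-exposure data. It keeps everything collected before exposure, including the Visit 3 SIQ and the re-enrolment C-SSRS, and treats later C-SSRS, SIQ, IAT and ETB values as missing.

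The cost is wording in two sections, one dated flag, and possibly a matching change to the consent form, since withdrawal circumstances are stated there. A few participants would receive the open-training offer later, and any sessions after Visit 5 would need scanner time outside the five-visit schedule. Section 17.1 promises no benefit from the training, and the safety procedures in section 16 are unaffected. If the sponsor meant only completion of the assigned sessions, the amendment simply writes that down.

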16.1 Foreseeable Risks

1. **Suicide attempt or completion risk.** Because the focus of this study is an intervention for **participants with recent suicide attempts and current suicide ideation**, the participants are at increased risk for suicide attempts, increased suicide thoughts and hospitalizations. **Participants who have attempted suicide are more likely to repeat attempts, to be hospitalized or to complete suicide compared to the general population of psychiatric patients. It is highly likely that the present study will entail reporting suicide attempts, suicide completions and hospitalizations given the population we are studying. Suicide attempts, completions or hospitalizations are thus a characteristic of the population and not a likely consequence of the proposed intervention which is of minimal risk and intrusiveness.**

2. In person suicide risk will be assessed at baseline and at the post-intervention assessment and additional precautions will be taken to help ensure participant safety. The PI ([name], PhD, L.P.) will work in conjunction with a designated pediatric psychiatrist at the Department of Psychiatry Child and Adolescent Clinic. [name] or the designated pediatric psychiatrist (if the PI is on vacation or in a conference) will be available to the PI and study staff during each of the clinical assessments, to consult with the study staff regarding the suicide risk, triage, and intervention planning. In addition to these resources, the UMN outpatient clinic has a list of 6 qualified providers that experimenters can call in case of emergency. During in-person assessments, if a 72-hour hold is warranted to ensure participants safety, security personnel are readily available in case experimenters determine that there is urgent need for escorting participants and families to the emergency department (ED) for possible hospitalization and/or further evaluation.

3. **Potential loss of confidentiality.** All clinical information will be kept confidential in a secure database. Data will be stored using a study-generated identification number. Any documents with personal health information (i.e., consent forms), will be kept in a separate, locked file. Links between participant names and participant numbers will be stored in a secure database with limited access only to select study staff. Information provided by the Participants to study staff will be kept confidential from their parents, except in the case where danger to self or others is identified. In those cases, the parents will be informed, and the participant will be referred to clinically appropriate emergency care.

4. **Distress related to clinical assessments and neurofeedback.** Some of the questions may be distressing to Participants and young adults with internalizing symptoms because of inducing low levels of negative self-focused cognitions. Additionally, anxious individuals can easily feel overwhelmed or fatigued by what would be minimally demanding tasks for others, such as filling out these assessments. Voluntary neuromodulation is not easy, some participants may feel frustrated or sad due to perceived inability to complete the task.

5. **Risks related to MRI**

- a. ***Claustrophobia.*** Some people experience fear while inside the scanner due to its confining space.
- b. ***Magnetic pull-on metal objects.*** The strong magnetic field in the scanner could cause any foreign metal bodies implants in the participants to change position, injuring them.
- c. ***Scanner noise.*** The noise generated from the operation of the scanner is loud and can damage hearing without protection.
- d. ***Mild symptoms.*** Some people experience mild, short-term symptoms while in the scanner, including headaches, dizziness, mild nausea, metallic taste, and/or the sensation of flashing lights. These symptoms resolve shortly after removal from the magnetic field.
- e. ***Boredom.*** MRI scans involve a large time commitment, and participants may become bored.
- f. ***Potential for discovery of brain abnormalities.*** It is possible that the MRI scan would reveal unknown and unlooked for abnormalities. We will refer the family to a radiologist (covered by the family's insurance) and provide them with a copy of the structural images if so desired.
- g. ***Energy from the scanner can cause heating or nerve stimulation.*** The power of the energy waves from the scanner is well below the strength needed to heat body tissues and cause harm, but any metal in contact with the participant's skin could cause heating. It is also possible that the scanner will cause peripheral nerve stimulation (stimulation of the nerves or muscles).

6. New psychiatric disorders. Participants will be assessed for a variety of symptoms, and it may be determined that the participant meets the criteria for a psychiatric disorder that they were not already being treated for.

7. Onset or worsening of symptoms due to medication: The population been studied is likely to be taking one or several psychotropic medications. The proposed intervention will not change or manage participant's medications and the investigators will not directly attempt to solve issues related to medication management.

16.2 Suicide Risk Management in Person.

[name], PhD, LP (PI) will always be on call when a participant is being evaluated in person, or she will arrange for other providers (CoI 1 or [name]) to be on call. Additionally, other providers (such as social workers or medical residents) that are generally “on call” could be reached by the staff to evaluate acute suicide ideation (The psychiatry department will internally decide the mechanism about fast communication into the administrating attending).

A psychiatrist or psychologist will be available to the study staff and PI as a consultant if high risk suicidal thoughts or behaviors are identified. The psychiatrist or psychologist will be the key person aiding the PI's evaluation of the need for hospitalization. This individual will complete additional assessment as necessary either by phone or in person. [name] or the psychologists/psychiatrist will collaborate with the study team, participant, and family to construct an appropriate safety plan (Stanley & Brown Safety Plan) and will facilitate referrals for appropriate follow-up psychiatric care. **Figure 1** summarizes the suicide risk assessment and action protocol, which includes comprehensive suicide risk assessment, clinical formulation, and triage, followed by level of care and suicidal risk level determination (see Figure 1).⁵² This in-depth assessment will involve the parents to inform them of the current level of risk, gather information regarding the current safety of the home environment and an understanding of current supports, and engage them in safety planning.

If imminent suicide attempt is suspected during the risk assessment, the study staff will contact [name] or the designated psychologist/psychiatrist who will: 1. Contact the participant and their caregivers and re-evaluate intent, plan and lethality using the C-SSRS, the Modified Scale for Suicidal Ideation, and the Stanley Brown Safety Plan. 2. Consult with other providers or with available staff at the University of Minnesota clinic and determine if hospitalization is needed. 3. In the case of significant risk, parents will be informed and involved in the safety planning. All research staff members will be trained according to and follow this protocol.

During in person assessment, emergency medical care (EMC) is available for all research participants at the University of Minnesota Medical Center (UMMC) including security personnel to escort participants and their families to the ED. Participants and their parents will be escorted to the ED by qualified research personnel (The PI, a postdoctoral licensed clinical psychologist, or equally qualified personnel will supervise and conduct these procedures).

16.3 Suicide risk management for enrolled participants.

In between study sessions, and as part of the Stanley-Brown Safety Plan, some enrolled participants will be able to call or text the PI ([name], CoI 1 or any accredited mental health professional) on a cellphone if they feel that the measures in the safety plan are ineffective and they are in impending danger of attempting suicide. Families, parents, caregivers, and participants will be encouraged to save the emergency study phones as “**Emergency Teen Brain Training**” in their mobile devices so that they can easily reach us. The PI and accredited mental health professionals will save the participants number on their cellphone as “TBT-participant ID” (after consent and assent forms are signed) in order to be able to know who is calling and quickly respond. The participant would only be identifiable by ID number and no names would be linked to the participants’ phone numbers on personal cell phone devices. Participants and their parents will be told that emergency phone calls/texts will be returned by the PI or the psychologist/psychiatrist within **1 hour** (as the PI, accredited mental health professionals and/or psychologist/psychiatrist may be providing services to other patients); or as soon as the study staff can alert those clinicians or “on call” staffing accredited mental health professionals, of a participant’s suicide attempts risks; whichever time frame is shorter. Participants and their parents will be informed of such procedures in the consent and assent form.

However, if the calls, emails, or text are received during the night hours (e.g., after 9 pm) calls/text will not be answered until the next day, and they should call 911 or go to the nearest emergency room to keep themselves safe.

[figure not shown]

Figure 1: Adapted from Labouliere et al. (2018). This figure provides general guidance for clinicians in charge of at-risk participants. Procedures within a research project are different from some of the assumed timing in this figure because the programmed contact times during the research are different from an ongoing standard clinical practice (i.e., weekly psychotherapy or medication appointments). This plan, however, provides good general guidance for research staff to interact and assess participants' safety while actively enrolled in research.

